### 7.2 Statistical Analyses

#### 7.2.1 *General Approach*

- For descriptive statistics, categorical data will be presented as percentages and continuous data will be presented as medians with intraquartile ranges.
- All statistical tests will be 2-sided, with  $p < 0.05$  indicating statistical significance.

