## 1 STUDY SUMMARY

### 1.1 Synopsis

**Title:** PROSPECTIVE EVALUATION OF COMPUTED TOMOGRAPHY GUIDED MAPPING AND ABLATION OF CARDIAC GANGLIONATED PLEXI IN PATIENTS WITH ATRIAL FIBRILLATION

**Short Title:** CT Guided Ablation of Ganglionated Plexi

**Study Description:** Single-arm prospective study to evaluate the role of high frequency stimulation (HFS) and computed tomography (CT) guided mapping and ablation of ganglionated plexi (GP) in patients with atrial fibrillation.

**Objectives:** Primary:

Secondary:

To assess the effects of GP ablation on local HFS response and global vagal stimulation in order to characterize the neural pathways connecting GPs

**Primary Endpoint:** The primary outcome of interest will be the successful identification of GP signals by high frequency stimulation and anatomic correlation between these points and CT identified epicardial adipose tissue within 3 pixels ( $0.625 \times 3 = 1.875$ mm).

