**Secondary Endpoints:**

[figure not shown]
- Elimination of local of HFS response following GP ablation
- Elimination of global vagal response to non-invasive ear stimulation
- Characterization of amplitude, duration, and fractionation of signals at sites with HFS responses and successful HFS elimination

**Study Population:** 19 patients with atrial fibrillation undergoing catheter ablation of atrial fibrillation

**Description of Sites/Facilities** All ablation procedures will be performed at the Hospital of the University of Pennsylvania.

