### **2.3.3 Assessment of Potential Risks and Benefits**

The risks of participating in the study are not significant beyond the risks associated with routine clinical care (including pre-procedural CT imaging, atrial mapping and ablation). Therefore, the potential benefits to the individual subject and to society outweigh the risks of participating in the study.

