## 7 STATISTICAL CONSIDERATIONS

### 7.1 Statistical Hypotheses

- Primary Efficacy Endpoint(s): We anticipate anatomic correlation between CT identified epicardial adipose tissue within 3 pixels ( $0.625 \times 3 = 1.875\text{mm}$ ) of an endocardial mapping point where HFS confirmed a vagal response consistent with ganglionated plexus innervation.
- Secondary Efficacy Endpoint(s): Acute procedural success defined by elimination of ear vagus nerve stimulation response will be achievable in all patients.

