#### **7.2.4 Safety Analyses**

A summary statistic for all adverse events will be reported. All adverse events will be presented based on severity, frequency, and relationship to study intervention. Adverse events leading to premature discontinuation from the study intervention and serious treatment-emergent AEs will be separately listed.

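### The secondary hypothesis of acute success in every patient has no reference rate or planned interval, and 19 patients in one arm cannot establish it

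*Combined protocol and SAP*

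**What the plan says.** The Synopsis (1.1) describes a "Single-arm prospective study to evaluate the role of high frequency stimulation" and CT-guided mapping and ablation of ganglionated plexi, in "19 patients with atrial fibrillation undergoing catheter ablation of atrial fibrillation". The text gives no sample-size or precision rationale for 19.

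The secondary hypothesis in 7.1 reads: "Acute procedural success defined by elimination of ear vagus nerve stimulation response will be achievable in all patients". No null rate, minimum acceptable rate or decision rule goes with it. Section 6.1 counts this elimination among the measures of acute procedural efficacy.

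On analysis:

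- 7.2.1, speaking of descriptive statistics, says that "categorical data will be presented as percentages and continuous data will be presented as medians with intraquartile ranges". It adds "All statistical tests will be 2-sided" with a 0.05 threshold, but assigns no test to acute success.
- 7.2.3, the section on secondary endpoints, defines AF burden and does not mention acute success.
- 7.2.4 says "A summary statistic for all adverse events will be reported". It goes on to plan presentation by severity, frequency and relationship, with separate listings of serious treatment-emergent events and of events leading to discontinuation.
- No section plans a confidence interval for any proportion.

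Section 4.8.1 has the response to ear stimulation documented before ablation. It does not say how a patient with no response at baseline enters the elimination endpoint.

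**The concern.** A claim about all patients cannot be confirmed by a sample. Any number of successes is compatible with a true rate below 100%, and a single failure contradicts the claim as worded. Testing at p < 0.05 does not help, because a single arm with no reference rate leaves nothing to test against, and 100% is not a usable null value.

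That leaves a percentage from at most 19 patients as the only specified form of result, with no statement of its precision. Precision is the main limitation of a study this small. The plan should therefore say how uncertainty will be shown, and which patients form the denominator, before the data are seen.

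The same gap affects the adverse event proportions in 7.2.4, where a low or zero count from 19 patients carries wide uncertainty.

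**Working it through.** **Inputs.** N = 19 and single arm (Synopsis); target of all patients (7.1); percentages as the descriptive format (7.2.1). The documents give no power, reference rate or interval width, so there is no figure of the plan's own to reproduce. The true success and event rates below are assumptions, shown as a range.

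**Step 1: what a perfect result supports.** For n successes out of n, the exact (Clopper-Pearson) two-sided 95% lower limit L solves Lⁿ = 0.025, so L = 0.025^(1/n).

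- n = 19: 0.025^(1/19) = 0.824, so 19/19 gives 82.4% to 100%. The Wilson lower limit, as a check, is 83.2%.
- n = 16 (assumed, if three patients are not evaluable): 0.025^(1/16) = 0.794, so 16/16 gives 79.4% to 100%.

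**Step 2: one failure.** For 18/19 = 94.7%, the lower limit is the 0.025 quantile of Beta(18, 2) = 0.740. The upper limit is the 0.975 quantile of Beta(19, 1) = 0.975^(1/19) = 0.999. The interval is 74.0% to 99.9%.

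**Step 3: how often at least one failure occurs.** With true success rate p and 19 independent patients, P(19/19) = p^19 and P(at least one failure) = 1 − p^19.

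| Assumed p | P(19/19) | P(at least one failure) |
|---|---|---|
| 0.90 | 13.5% | 86.5% |
| 0.95 | 37.7% | 62.3% |
| 0.98 | 68.1% | 31.9% |
| 0.99 | 82.6% | 17.4% |

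The two outcomes are equally likely at p = 0.5^(1/19) = 0.964.

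**Step 4: adverse events.** For zero events in n patients, the upper limit is 1 − 0.025^(1/n).

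- n = 19: 1 − 0.824 = 0.176, so 0/19 gives 0% to 17.6%.
- If the true event rate were 5%, no events would be seen with probability 0.95^19 = 37.7%. At 10% it would be 0.90^19 = 13.5%.

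These limits concern the total event rate in the one arm. With no comparator they say nothing direct about the increment over routine ablation.

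**The case against.** The strongest reply is that this is a small observational study of feasibility and efficacy (4.1). On that view the wording of 7.1 is an expectation and not a test, no stopping or treatment decision hangs on it, and anyone given n/N can compute an interval. Much of that stands. The plan contains no pass/fail rule, so the probabilities in step 3 describe a literal reading of 7.1, not a planned test. A missing interval also biases nothing. For these reasons the point is minor. It still has force, because 7.1 offers no other criterion and 7.2.3 gives no analysis of the endpoint.

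Four stronger readings are tempting, and the documents do not support them.

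- *A reader might infer that 19/19 would be reported as proof of 100%, or 0/19 as showing no added risk.* No section says so. The statement in 2.3.3 that "The risks of participating in the study are not significant beyond the risks associated with routine clinical care" is a risk/benefit judgement made in advance, not a conclusion to be drawn from the data, and 7.1 has no safety hypothesis.
- *A reader might infer that a very effective procedure would probably fail the hypothesis.* That holds only below a true success rate of about 96.4%. At 98% or 99%, 19/19 is the likelier outcome.
- *A reader might infer that safety receives a single summary statistic.* Section 7.2.4 plans several tabulations and listings beyond its opening sentence.
- *A reader might infer that 7.2.1 restricts endpoint results to bare percentages.* Its sentence sets the descriptive format. The gap is that no other analysis of this proportion appears anywhere.

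**Conclusion.** The concern holds as a minor point. The secondary hypothesis is worded as a 100% claim with no reference rate, no test and no specified analysis, and the plan includes no interval for any proportion. With all 19 patients evaluable, a perfect result supports a true rate of at least 82.4% (exact two-sided 95%), not 100%, and 18/19 gives 74.0% to 99.9%. Read literally, the hypothesis would be contradicted with probability 62%, 32% or 17% if true success were 95%, 98% or 99%.

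The interval limits rest on 19 evaluable patients. If patients without a baseline ear response are excluded, the denominator falls and the limits widen. The probabilities also assume independent patients and the stated true rates, none of which come from the documents. The conclusion that 19 patients cannot establish 100% depends on none of these assumed rates.

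**What to change.** - **7.1 and 7.2.3:** restate the secondary hypothesis as estimation of the proportion of patients with elimination of the ear-stimulation response, among those with a documented baseline response. Report it as n/N with an exact (Clopper-Pearson) two-sided 95% interval. Illustrate the precision for a range of evaluable n (for example, a lower limit of 82.4% for 19/19 and 79.4% for 16/16), without fixing one figure in advance.
- **7.2.1:** report each patient-level endpoint percentage with n/N and its exact 95% interval.
- **7.2.4:** keep the planned tabulations and listings. Add the same interval to the proportions of patients with any related adverse event and with any serious adverse event. State that it bounds the total event rate in this arm and not the risk added over routine ablation.

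The cost is a few lines of text and one extra table column, with no new patients, data or procedures. The stated claim becomes somewhat less favourable.

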#### 7.2.2 *Analysis of the Primary Efficacy Endpoint(s)*

- Anatomic correlation between CT and GP mapping will be defined based on review of electroanatomic maps from the ablation procedure merged with segmented pre-procedural CT images.

#### 7.2.3 *Analysis of the Secondary Endpoint(s)*

- AF burden will be defined based on loop recorder interrogation and patient history of requiring cardioversion

#### **7.2.4 Safety Analyses**

A summary statistic for all adverse events will be reported. All adverse events will be presented based on severity, frequency, and relationship to study intervention. Adverse events leading to premature discontinuation from the study intervention and serious treatment-emergent AEs will be separately listed.

#### **7.2.5 Baseline Descriptive Statistics**

Patients will be compared based on baseline characteristics, including demographics and laboratory measurements, using descriptive statistics including Chi-squared tests for categorical variables, and analysis of variance for continuous variables. All statistical tests will be 2-sided, with  $p<0.5$  indicating statistical significance.

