#### **7.2.6 Sub-Group Analyses**

Primary and secondary endpoints will be analyzed based on age, sex, race/ethnicity or other demographic characteristic(s).

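### Section 7.2.5 sets the significance threshold for all tests at p<0.5, against p<0.05 in section 7.2.1: very probably a dropped zero, and a one-line correction

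*Combined protocol and SAP*

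**What the plan says.** The combined protocol and SAP states a significance threshold twice.

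- Section 7.2.1 (General Approach): "All statistical tests will be 2-sided, with $p < 0.05$ indicating statistical significance".
- Section 7.2.5 (Baseline Descriptive Statistics): "All statistical tests will be 2-sided, with $p<0.5$ indicating statistical significance".

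The second sentence directly follows the plan for the baseline data. There, "Patients will be compared based on baseline characteristics", with chi-squared tests for categorical variables and analysis of variance for continuous ones. Section 7.2.1 separately says how descriptive data are to be shown: "categorical data will be presented as percentages and continuous data will be presented as medians with intraquartile ranges". The Synopsis (section 1.1) describes a "Single-arm prospective study" and gives a study population of 19 patients.

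**The concern.** Each sentence claims to govern every test in the study, so 7.2.5 cannot be read as a deliberate local rule for baseline variables. The plan therefore holds two incompatible decision rules, gives no reason for the 0.5 and has no order of precedence.

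The tests most directly affected are the chi-squared and analysis-of-variance comparisons in 7.2.5, because the 0.5 is attached to them. At that threshold, chance differences would routinely be reported as significant. Section 7.2.6 plans subgroup analyses of the primary and secondary endpoints without a threshold of its own, so any test run there also faces two stated values.

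**Working it through.** **1. The two statements side by side**

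| | Section 7.2.1 | Section 7.2.5 |
|---|---|---|
| Scope | all statistical tests | all statistical tests |
| Sidedness | 2-sided | 2-sided |
| Threshold | 0.05 | 0.5 |
| Critical absolute z | 1.960 | 0.674 |
| Critical chi-squared, 1 df (z squared) | 3.841 | 0.455 |

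The ratio is 0.5 / 0.05 = 10. One-sided against two-sided testing does not explain it, since both are 2-sided. The documents describe no multiplicity split or interim look that could explain it either.

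**2. What depends on the threshold**

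- Primary analysis (7.2.2): no test is named. The section says only that anatomic correlation "will be defined based on review of electroanatomic maps from the ablation procedure" merged with the segmented CT images.
- Secondary analysis (7.2.3): no test is named. The only content is "AF burden will be defined based on loop recorder interrogation and patient history of requiring cardioversion".
- Sample size: the 19 patients are not derived from any alpha or power in the available text, so the number does not change under either threshold.
- Baseline comparisons (7.2.5): tests are named, and the 0.5 is attached to them.
- Subgroups (7.2.6): neither a test nor a threshold is given.

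**3. Size if 7.2.5 is applied literally**

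Expected false positives among k true-null comparisons = k × alpha. The documents do not give k, so the values below are assumptions.

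| k (assumed) | at 0.5 | at 0.05 |
|---|---|---|
| 5 | 5 × 0.5 = 2.5 | 5 × 0.05 = 0.25 |
| 10 | 10 × 0.5 = 5 | 10 × 0.05 = 0.5 |
| 20 | 20 × 0.5 = 10 | 20 × 0.05 = 1.0 |

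The chance of at least one false positive is 1 − (1 − alpha)^k if the comparisons are independent. For k = 10 this is 1 − 0.5^10 = 99.9% at 0.5, and 1 − 0.95^10 = 40.1% at 0.05. Baseline variables are usually correlated. Correlation leaves the expected counts unchanged but alters these at-least-one figures.

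**4. Does the nominal rate hold at 19 patients?**

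A chi-squared test on so few patients does not deliver its nominal rate exactly. The actual rate under the null can be enumerated for a 2×2 table: sum the product of two binomial probabilities over every table whose chi-squared statistic exceeds the critical value, counting tables with an empty margin as not significant. The plan names no groups, so the two-group splits (9/10, 6/13, 4/15) and the common proportions (0.2, 0.3, 0.5) are assumptions. The ranges below cover all nine combinations.

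| Chi-squared version | at 0.5 | at 0.05 |
|---|---|---|
| Uncorrected | 0.499 to 0.576 | 0.044 to 0.065 |
| Continuity-corrected | 0.170 to 0.280 | 0.004 to 0.019 |

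The uncorrected test stays close to its nominal rate. The continuity-corrected test falls well below it at both thresholds, but under 0.5 it still flags at least 17% of null comparisons.

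**5. After correction**

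With 0.05 in 7.2.5, the two sections agree exactly. No other figure in the plan moves.

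**The case against.** The strongest objection is that almost nothing in the plan can be harmed. The study has one arm and 7.2.5 names no groups, so its tests cannot be run as specified. The nearest thing to groups is the site of initial ablation, which section 4.2 allocates equally across 8 locations. That gives about 19 / 8 = 2.4 patients per site, and 7.2.5 does not link its comparisons to it. The false-positive rates above therefore describe comparisons that the plan never defines, with assumed splits, proportions and numbers of tests. This stands. It is why the finding is minor and why the rates should be read as illustration.

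A second objection is that an analyst would in practice follow the conventional value in the general section, for the subgroups as well. That is likely, but it leaves the reader to choose between two sentences with the same claimed scope.

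Third, the digit might have been lost when the PDF was read by program. This cannot be fully excluded, and the source file should be checked. However, the expression in 7.2.5 is well formed and nothing in the supplied text points to a reading error.

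None of these removes the contradiction.

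**Conclusion.** The inconsistency is real: the plan gives two thresholds, tenfold apart, for the same set of tests. That 0.5 is a slip for 0.05 is an inference, but a strong one, because the sentences are otherwise the same, the general section carries the conventional value and nothing supports 0.5.

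Read literally, the nominal false-positive rate per null baseline comparison is 50% instead of 5%. This figure follows from the thresholds alone. The expected counts and the exact rates at 19 patients rest on the assumptions stated with them.

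No primary or secondary conclusion in the available text depends on the value, so the severity is minor. Confidence in the contradiction is high, subject to the check against the source file.

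**What to change.** Check the source file. If it reads 0.5, either change it to 0.05 in section 7.2.5, or delete the sentence there and refer to 7.2.1. Deleting is slightly better, because the threshold then stands in one place only.

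Correcting the digit does not settle the separate matter of the undefined groups. Either name the groups that 7.2.5 is meant to compare, or drop the tests and summarise baseline data as 7.2.1 already describes, with percentages and with medians and interquartile ranges (the text has a slip in that term too).

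The cost is a text correction of one line, or a few lines if the tests are dropped. Data collection, sample size and timelines are unaffected.

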#### **7.2.6 Sub-Group Analyses**

Primary and secondary endpoints will be analyzed based on age, sex, race/ethnicity or other demographic characteristic(s).

#### **7.2.7 Tabulation of Individual Participant Data**

Individual participant data will not be listed by measure and time point.

## 8 SUPPORTING DOCUMENTATION AND OPERATIONAL CONSIDERATIONS

### 8.1 Regulatory, Ethical, and Study Oversight Considerations

#### 8.1.1 *Informed Consent Process*

##### 8.1.1.1 *Consent/Accent and Other Informational Documents Provided To Participants*

Consent forms describing in detail the GP mapping and ablation study procedures, and risks are given to the participant and written documentation of informed consent is required prior to enrollment. The following consent materials are submitted with this protocol: Consent and HIPAA authorization form.

##### 8.1.1.2 *Consent Procedures and Documentation*

Informed consent is a process that is initiated prior to the individual's agreeing to participate in the study and continues throughout the individual's study participation. Consent forms will be Institutional Review Board (IRB)-approved and the participant will be asked to read and review the document. The investigator will explain the research study to the participant and answer any questions that may arise. A verbal explanation will be provided in terms suited to the participant's comprehension of the purposes, procedures, and potential risks of the study and of their rights as research participants. Participants will have the opportunity to carefully review the written consent form and ask questions prior to signing. The participants should have the opportunity to discuss the study with their family or surrogates or think about it prior to agreeing to participate. The participant will sign the informed consent document prior to any procedures being done specifically for the study. Participants must be informed that participation is voluntary and that they may withdraw from the study at any time, without prejudice. A copy of the informed consent document will be given to the participants for their records. The informed consent process will be conducted and documented in the source document (including the date), and the form signed, before the participant undergoes any study-specific procedures. The rights and welfare of the participants will be protected by emphasizing to them that the quality of their medical care will not be adversely affected if they decline to participate in this study.

### **8.1.2     *Study Discontinuation and Closure***

This study may be temporarily suspended or prematurely terminated by the Sponsor or the PI at any site if there is sufficient reasonable cause. Written notification, documenting the reason for study suspension or termination, will be provided by the suspending or terminating party to regulatory authorities. If the study is prematurely terminated or suspended, the Principal Investigator (PI) will promptly inform study participants, the Institutional Review Board (IRB), and sponsor and will provide the reason(s) for the termination or suspension. Study participants will be contacted, as applicable, and be informed of changes to study visit schedule.

Circumstances that may warrant termination or suspension include, but are not limited to:

- Determination of unexpected, significant, or unacceptable risk to participants
- Demonstration of efficacy that would warrant stopping
- Insufficient compliance to protocol requirements
- Data that are not sufficiently complete and/or evaluable
- Determination that the primary endpoint has been met
- Determination of futility

Study may resume once concerns about safety, protocol compliance, and data quality are addressed, and satisfy the sponsor, IRB and/or Food and Drug Administration (FDA).

In terminating the study, the Sponsor and the Principal Investigator will assure that adequate consideration is given to the protection of the subjects' interests.

### **8.1.3      Confidentiality and Privacy**

Participant confidentiality and privacy is strictly held in trust by the participating investigators, their staff, and the sponsor(s) and their interventions. This confidentiality is extended to cover testing of biological samples and genetic tests in addition to the clinical information relating to participants. Therefore, the study protocol, documentation, data, and all other information generated will be held in strict confidence. No information concerning the study or the data will be released to any unauthorized third party without prior written approval of the sponsor.

All research activities will be conducted in as private a setting as possible.

The study monitor, other authorized representatives of the sponsor, representatives of the Institutional Review Board (IRB), regulatory agencies or pharmaceutical company supplying study product may inspect all documents and records required to be maintained by the investigator, including but not limited to, medical records (office, clinic, or hospital) and pharmacy records for the participants in this study. The clinical study site will permit access to such records.

The study participant's contact information will be securely stored at each clinical site for internal use during the study. At the end of the study, all records will continue to be kept in a secure location for as long a period as dictated by the reviewing IRB, Institutional policies, or sponsor requirements.

Study participant research data, which is for purposes of statistical analysis and scientific reporting, will be transmitted to and stored in our Data Coordinating Center. This will not include the participant's contact or identifying information. Rather, individual participants and their research data will be identified by a unique study identification number. The study data entry and study management systems used by clinical sites research staff will be secured and password protected. At the end of the study, all study databases will be de-identified and archived.

